### **9.3.5. Retrospective Visit**

Any assessments listed in [Section 9.3.1](#) Study Assessments and performed prior to the patient's Eligibility/Baseline visit may be entered into the THAOS electronic data record as retrospective visit data. This data collection is optional.

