### Assessments

A series of assessments will be used to assess disease progression and the effects of tafamidis treatment including demographics, TTR genetic test results, tissue biopsy results, family disease history, medical history, annual medical assessment, general examination, concomitant medication use, hospitalizations, transplant history and complications related to transplantations, AE/SAE reporting for tafamidis-treated patients, health events of interest, clinical laboratory data, urinalysis, CCI [REDACTED], [REDACTED] neurologic assessments, eye examination, body composition, CCI [REDACTED], [REDACTED] and death.

Data will be collected at an eligibility/baseline visit, return visits, and in the form of status updates if the patient has not visited the site. In addition, pre-baseline retrospective data may optionally be captured.

Return visits will be conducted annually (on average) or at the discretion of the survey physician. The reporting window for collecting changes in signs, symptoms, AEs, and new diagnoses is from the last prior visit.

A final visit, including collection of AE/SAE information will be performed at the completion of the survey or at the time the patient elects to discontinue, whichever occurs first. For patients enrolled in interventional clinical trials that include open-label tafamidis or other open label investigational products, follow-up in THAOS may continue, but AE data collection and reporting will be addressed through the interventional clinical trial sponsor. If a patient dies while enrolled in the survey, the site is asked to collect all available information related to the death.

If a patient enrolls in a double blind investigational clinical trial or any other trial (including Tafamidis Compassionate Use/Early Access Program) during the course of their follow-up in THAOS, data collected for such patients (if included in the THAOS database) will be excluded from analyses specified within this SAP.

AE/SAE data collected in THAOS will be used to further characterize the safety profile of tafamidis and as a result, to fulfil certain aspects of the European Union (EU) post-

marking commitment for tafamidis. Based on the safety concerns detailed in Table 1, corresponding data for Health Events of Interest will be summarized to characterize both the natural history of ATTR amyloidosis in participants not treated with tafamidis and safety concerns amongst tafamidis-treated patients.

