**Table 2 Data Collection per Visit**

Case Report Form	Eligibility/ Baseline Visit	Return Visits	Retrospective Visits (optional)	Final Visit c
Written informed consent/assent	X	--	--	--
Inclusion/exclusion criteria	X	--	--	--

PFIZER CONFIDENTIAL

Case Report Form	Eligibility/ Baseline Visit	Return Visits	Retrospective Visits (optional)	Final Visit c
Patient demographics date of birth, gender, ethnic origin	X	--	--	--
Clinical trial and compassionate use program participation (log format)	X	X	X	
TTR data genetic test results, tissue biopsy	X	--	--	--
Family history of ATTR amyloidosis	X	--	--	--
Medical history past and current signs, symptoms and medical diagnoses	X	--	--	--
Annual updated medical assessment current signs and symptoms	--	X	--	X
General exam weight/height, vital signs, CCI [REDACTED]	X	X	X	X
Concomitant medications (log format) category, indication, start and stop dates	X	X	X	X
Tafamidis treatments (log format) dose, start and stop dates	X	X	X	
Hospitalizations (log format) admission and discharge dates, reason for hospitalization	--	X	X	X
Transplant history and complications (log format) date(s) of transplant(s), organ(s) transplanted, information on complications	X	X	X	X
Adverse events	X	X	X	X
Laboratory data Hematology, clinical chemistry, urinalysis, including glomerular filtration rate [GFR]	X	X	X	X
CCI [REDACTED]	■	■	■	■
[REDACTED]	■	■	■	■
Nerve conduction studies: Upper Extremity, Lower Extremity				
Renal/bladder ultrasound a residual volume, number and size of kidneys, echogenicity	X	X	X	X

Case Report Form	Eligibility/ Baseline Visit	Return Visits	Retrospective Visits (optional)	Final Visit c
Eye examination a intraocular pressure, vitreous, presence of opacities	X	X	X	X
Body composition a total bone mineral density and content, total lean and fat mass	X	X	X	X
CCI [REDACTED]	■	■		X
Patient death b			X	
Patient discontinuation b			X	
Patient status update b			X	

a Printed assessment worksheets will be available to provide to outside specialists performing assessment(s).

b Data on patient deaths, discontinuations, and status assessments will be collected independent of the visit schedule.

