## 5.2 TAFAMIDIS UNTREATED

The tafamidis untreated set will include the following:

- All available data from patients who have been enrolled in THAOS, signed the informed consent and who have not received tafamidis during the THAOS study.
- All available data before receiving the first dose of tafamidis while in THAOS, for those patients who were not on tafamidis during or after initial enrollment in THAOS but then started receiving tafamidis post enrollment.

Note: Available data after a patient discontinues treatment with tafamidis will be excluded (See Figure 1)

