### Blood Pressure

Change from baseline by yearly intervals of the systolic and diastolic blood pressure will be provided using tafamidis treated set by starting dose and tafamidis untreated set.

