### Electrocardiogram

For ECG, the following summaries will be provided at baseline and by yearly intervals:

- Any abnormalities in rhythm (Y/N)
- Sinus pause (Y/N)
- Atrial flutter (Y/N)

- Atrial fibrillation (Y/N)
- Atrial premature beat (Y/N)
- Junctional rhythm (Y/N)
- Ventricular tachycardia (Y/N)
- Ventricular premature complexes (Y/N)
- Other rhythm abnormality (Y/N)
- Pacemaker with normal function (Y/N)
- Low voltage (Y/N)
- Conduction abnormalities(Y/N)
- Types of conduction abnormalities
- Morphology abnormalities
- Types of morphology abnormalities
- Pathologic Q-Waves observed
- Types of P-Q wave abnormalities
- ST Segment T Wave abnormalities
- Types of ST Segment abnormalities

Also for the following parameters corresponding to ECG, summary statistics for the baseline and change from baseline by yearly intervals will be provided:

- QRS Axis
- PR
- QRS
- QT
- QTc

The summaries will be done using the tafamidis untreated set with predominantly cardiac or mixed phenotype at enrollment, tafamidis treated set with predominantly cardiac or mixed phenotype at enrollment, CCI [REDACTED] and either predominantly cardiac or mixed phenotype at enrollment, tafamidis treated set for patients who switched from predominantly neurologic to mixed phenotype and tafamidis untreated set for patients who switched from predominantly neurologic to mixed phenotype.

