## APPENDIX 2: DATA DERIVATION DETAILS

### A1.1 Definition and use of visit windows in reporting

For All enrolled set and tafamidis untreated set (as well as the subgroups corresponding to untreated set), Day 1 will be the most recent available value collected either on or after the informed consent signed date. The study day will be calculated as follows:

Study day = assessment date – consent date

For the tafamidis treated set (as well as the subgroups corresponding to treated set), Day 1 will be the most recent available value collected either on or after the first dose of tafamidis received after enrollment in THAOS. The study day will be calculated as follows:

Study day = assessment date – date of first dose of tafamidis after enrollment in THAOS / consent date if patient was continuing taking tafamidis prior to enrollment (whichever is earlier) + 1

The following visit window will be applied, considering the absolute value of study day (absday):

Condition	Visit	Year
$\text{absday} < -365.25 \times 0.5$	-1	
$0 \leq \text{absday} \leq 365.25 \times 0.5$	0	
$365.25 \times 0.5 < \text{absday} \leq 365.25 \times 1.5$	1	1
$365.25 \times 1.5 < \text{absday} \leq 365.25 \times 2.5$	2	2
$365.25 \times 2.5 < \text{absday} \leq 365.25 \times 3.5$	3	3
$365.25 \times 3.5 < \text{absday} \leq 365.25 \times 4.5$	4	4
$365.25 \times 4.5 < \text{absday} \leq 365.25 \times 5.5$	5	5
$365.25 \times 5.5 < \text{absday} \leq 365.25 \times 6.5$	6	6
$365.25 \times 6.5 < \text{absday} \leq 365.25 \times 7.5$	7	7
$365.25 \times 7.5 < \text{absday} \leq 365.25 \times 8.5$	8	8
$365.25 \times 8.5 < \text{absday} \leq 365.25 \times 9.5$	9	9
$365.25 \times 9.5 < \text{absday} \leq 365.25 \times 10.5$	10	10
$365.25 \times 10.5 < \text{absday} \leq 365.25 \times 11.5$	11	11
$365.25 \times 11.5 < \text{absday} \leq 365.25 \times 12.5$	12	12

Note: If study day is missing, then visit will be considered as missing.

CCI [REDACTED]

	CCI [REDACTED]	[REDACTED]	[REDACTED] → [REDACTED]
CCI [REDACTED]	[REDACTED]	[REDACTED]	[REDACTED]
[REDACTED]	[REDACTED]	[REDACTED]	0 → 4 1 → 3.75 2 → 3.5 3 → 3.25 4 → 2 5 → 0
[REDACTED]	[REDACTED]	[REDACTED]	Present → [REDACTED] [REDACTED] → [REDACTED]
[REDACTED]	[REDACTED]	[REDACTED]	Normal → [REDACTED] Decreased → [REDACTED] Absent → [REDACTED]
CCI [REDACTED]	[REDACTED]	[REDACTED]	[REDACTED]

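### Visit windows use the absolute value of study day, so Visit -1 cannot occur and readings from 183 to 4,565 days before consent are labelled follow-up Years 1 to 12

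*SAP*

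**What the plan says.** For the all-enrolled and untreated sets, SAP Appendix 2, A1.1 defines study day as assessment date minus consent date, so it is negative before consent. It then instructs: "The following visit window will be applied, considering the absolute value of study day (absday". The table below has a Visit -1 row for values under -365.25 × 0.5 with its Year cell blank, a Visit 0 row from 0 to 365.25 × 0.5, and rows for Years 1 to 12 in steps of 365.25 days. The only note after the table concerns a missing study day.

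Other places decide whether pre-consent readings can reach this table:

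- SAP 2.1, Assessments: "In addition, pre-baseline retrospective data may optionally be captured".
- Protocol 9.3.5: any assessment in the 9.3.1 list done before the baseline visit "may be entered into the THAOS electronic data record as retrospective visit data". That list includes vital signs and the electrocardiogram.
- SAP Table 2: the general exam row ("weight/height, vital signs") is marked for retrospective visits.
- SAP 5.2, first bullet: "All available data from patients who have been enrolled in THAOS, signed the informed consent and who have not received tafamidis during the THAOS study". No lower date limit is given.
- SAP 8.2: baseline for the all-enrolled and untreated sets is the latest visit no later than consent.

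The outputs by yearly interval are in SAP 8.2.6. Change in "systolic and diastolic blood pressure will be provided using tafamidis treated set by starting dose and tafamidis untreated set" is reported by year. For five ECG parameters, "summary statistics for the baseline and change from baseline by yearly intervals will be provided", and the other ECG items are summarised at baseline and by year.

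**The concern.** The instruction and the table contradict each other: a row for negative values cannot apply to a quantity that is never negative. If the instruction is programmed as written, time before consent is folded onto time after consent. A blood pressure taken a year before consent enters the Year 1 follow-up summary, and its difference from baseline is counted as follow-up change.

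Under a steady trend, a mirrored reading's change has the opposite sign to true follow-up change, so the two pull against each other. For the yes/no and categorical ECG items no sign reverses, but readings from earlier in the disease are mixed into later years. This falls in the untreated set, where the course of disease without tafamidis is described, and SAP 8.1 names natural history and progression as key objectives.

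The treated set is largely spared, because SAP 5.3 starts its data at enrollment or first dose. All analyses are descriptive (SAP 4), so no test or error rate is affected.

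**Working it through.** **Inputs.** All come from SAP A1.1. Study day d = assessment date - consent date (all-enrolled and untreated sets). Half-year cut: 365.25 × 0.5 = 182.625. Year k covers 365.25 × (k - 0.5) < value ≤ 365.25 × (k + 0.5). The upper limits are 547.875 for Year 1, 913.125 for Year 2, 1278.375 for Year 3 and 4565.625 for Year 12; Year 12 starts above 365.25 × 11.5 = 4200.375.

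**Step 1: label every whole day under three rules.**

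| Study day d | Absolute value, as written | Printed rows on signed day | Signed day, Visit 0 extended |
|---|---|---|---|
| -4565 to -4201 | Year 12 | Visit -1 | Visit -1 |
| -1278 to -914 | Year 3 | Visit -1 | Visit -1 |
| -913 to -548 | Year 2 | Visit -1 | Visit -1 |
| -547 to -183 | Year 1 | Visit -1 | Visit -1 |
| -182 to -1 | Visit 0 | no row | Visit 0 |
| 0 to 182 | Visit 0 | Visit 0 | Visit 0 |
| 183 to 547 | Year 1 | Year 1 | Year 1 |

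Years 4 to 11 follow the same pattern.

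- As written, no day reaches Visit -1. The pre-consent days given a follow-up year number 4565 - 182 = 4,383. Days before -4565 match no row.
- On signed day with the printed rows, no pre-consent day is called follow-up, but the 182 days from -182 to -1 have no label. This is only a labelling gap, because SAP 8.2 defines baseline separately.
- With Visit 0 extended, no pre-consent day is called follow-up and none is unlabelled. Compared with the rule as written, the 4,383 mirrored days move to Visit -1, as do days before -4565, which had no label. Days 0 to 4565 have the same label under all three rules.

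**Step 2: treated set.** Its study day adds 1. A baseline value 21 days before starting tafamidis, the earliest SAP 8.2 allows, has study day -21 + 1 = -20. Since 20 ≤ 182.625, it is Visit 0 both as written and under the extended signed rule.

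**Step 3: effect on a yearly mean.** Take one patient with steady change b per year, readings at days -365, 0 and +365, and baseline at day 0. The changes are (-365/365.25)b = -1.00b and (+365/365.25)b = +1.00b. As written, both are Year 1 and their mean is 0. On signed day the Year 1 value is +1.00b.

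More generally, let p be the share of Year 1 readings that are mirrored, with the same symmetric timing. The mean change is (1 - p)b + p(-b) = (1 - 2p)b. The documents do not give p, so these values are assumptions:

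| p | Year 1 mean change |
|---|---|
| 0 | 1.00b |
| 0.10 | 0.80b |
| 0.25 | 0.50b |
| 0.50 | 0 |

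**The case against.** The strongest reply is that the intention is plain. A Visit -1 row with no Year beside it shows that early pre-baseline readings were meant to stay outside the yearly intervals, and an empty Visit -1 would alert a programmer. A1.1 also ties Day 1 to a value on or after consent, and SAP 8.1 bases visit percentages on patients still in the study, which fits only post-enrollment visits. Retrospective entry is optional, so few readings may be involved.

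Much of this is fair. Mirroring was probably not intended, and harm needs literal programming, retrospective readings at least 183 days old, and no filter in code or redacted text. But neither the Day 1 sentence nor the percentage rule excludes any record, and the written instruction is explicit. The obvious alternative reading does not work cleanly either, since it leaves days -182 to -1 without a row.

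Two limits on the size of the effect also stand. Exact cancellation needs equal numbers of mirrored and true readings, averaged together; A1.1 as visible does not say how several records in one window are handled, and picking one per patient could give +b or -b. Sign reversal applies to blood pressure and the five continuous ECG parameters only, and nothing visible says these follow a steady trend.

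The all-enrolled set is the weaker part. The text of 8.2.6 gives it no yearly blood pressure or ECG table. The grid in SAP 8.2.8, as it reads in our text, marks all enrolled for blood pressure change, and also marks untreated for laboratory change, but neither mark matches the text of 8.2.6 and the grid may have been distorted in extraction.

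**Conclusion.** The concern holds. As written, Visit -1 cannot occur, and readings from 183 to 4,565 days before consent in the all-enrolled and untreated sets are labelled Years 1 to 12. The visible outputs at risk are the untreated-set yearly blood pressure and ECG summaries. The contradiction and the day ranges are certain. The resulting bias is not: it depends on literal programming and on an unstated share of retrospective readings, and it could be anywhere from near zero to a substantial dilution of the yearly change. Figure 1 and the redacted sections could not be checked for a rule that removes these readings. This should be corrected before the final report is programmed, because it is a stated derivation rule that gives wrong year labels.

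**What to change.** In A1.1, drop the absolute value and assign windows on signed study day:

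- below -182.625: Visit -1, kept out of the yearly summaries;
- -182.625 to 182.625: Visit 0;
- Years 1 onward: positive days only, with the present cut-offs.

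Dropping the absolute value alone is not enough; the Visit 0 row must also be extended, or days -182 to -1 have no label.

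The cost is the lead-in sentence, two table rows and their derivation code. The SAP's amendment table says the windows follow practice in earlier THAOS plans. If earlier outputs used the absolute value, yearly figures may differ from them, and one sentence in the report should say so.
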